114 b. If pooling is determined appropriate, evaluate objective 2 above within  
 115 appropriate pooling groups

116

117 **Natural History Study Objectives**

118 ***Within-Gene Objectives\****

119 The following objectives will be evaluated within gene.

120 **1. Natural History**

121 a. Characterize the natural history of retinal degeneration associated with disease-  
 122 causing genetic variants over 4 years, using functional, structural, and patient-  
 123 reported outcome measures

124 b. *Ideally where within-gene sample size is 20 or more*

125 **2. Structure-Function Relationship**

126 a. Explore whether structural outcome measures can be validated as surrogates for  
 127 functional outcomes in individuals with disease-causing genetic variants

128 b. *Ideally where within-gene sample size is 20 or more*

129

130 **3. Risk Factors for Progression**

- 131 a. Explore possible risk factors (genotype, phenotype, environmental, and  
 132 comorbidities) for progression of the outcome measures at 4 years in individuals  
 133 with disease-causing genetic variants  
 134 b. *Ideally where within-gene sample size is 40 or more*  
 135

136 \*Applicability of within-gene objectives will depend on within-gene sample size as noted above.  
 137 If less than 20, the primary objective will be limited to describing the cohort in the form of case  
 138 histories. Objectives may still be explored depending on the needs of a specific gene.  
 139

140 ***Across-Genes Objective***

141 The following objective will be evaluated across genes.

142 **4. Ancillary Exploratory Studies - Pooling of Genes**

- 143 a. Explore whether phenotype-genotype associations within biological mechanisms  
 144 or other factors (such as age or disease duration) will allow pooling of genes for  
 145 longitudinal analysis objectives

146 **1.4 Potential Risks and Benefits**

147 **1.4.1 Known Potential Risks**

148 Most examination procedures are considered part of standard care for retinal degenerations. This  
 149 study will be capturing some information about participants that include identifiable, personal  
 150 information, like date of birth (will be collected if permitted by site’s regulatory bodies). The  
 151 study has procedures in place to protect that information. However, there is a chance that a loss  
 152 of that protection could occur. This would be a loss of confidentiality. There are special efforts  

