 212 **Registry Cohort Criteria** (see section 2.6), unless the Executive Committee terminates  
 213 recruitment due to feasibility. The Executive Committee will monitor enrollment distributions  
 214 across genes, inheritance patterns, vision cohorts, and age cohorts with the planned caps as noted  
 215 below. Enrollment in some genes, inheritance patterns, vision cohorts, or age cohorts may be  
 216 encouraged to ensure appropriate representation, and some caps may be adjusted if needed.

- 217
- 218 • A **maximum of 100** participants will be enrolled within gene.
- 219 • Recruitment will be tracked within the three (3) vision cohorts as defined below:
  - 220 ○ A **maximum of 150** participants will be enrolled in Vision Cohort 3 (across
  - 221 genes).
  - 222 ○ Approximate target distribution of Vision Cohort 1 and 2 is 2:1 overall and within
  - 223 gene. This will be monitored and encouraged, but not required.
- 224 • A **maximum of 100** participants will be enrolled where Inheritance Pattern is Recessive
- 225 and phase is unknown.
- 226 • Participants will *not* be counted as ***enrolled into the Registry*** until **Genetic Screening**
- 227 **Criteria** have been confirmed (see section 2.5). This means that potentially more
- 228 participants will complete the Registry/Screening Visit than are ***enrolled into the***
- 229 ***Registry***. The number and reasons for screen failures will be tracked. It is possible that
- 230 some participants will have completed the Registry/Screening Visit and will be awaiting
- 231 genetic confirmation at the time the enrolled numbers reach the limits above. Therefore,
- 232 the actual enrolled numbers may be larger. To limit over-enrollment, clinical sites will be
- 233 notified as the recruitment limits are reached and efforts will be made to accurately
- 234 predict numbers in the genetic screening queue.

235 **2.2 Cohort Definitions**

236 **Vision Cohort Definitions**

Vision Cohort 1 Approximately 900 participants	Criteria that must be met in the better eye* at the Registry/Screening Visit: ○ visual acuity ETDRS letter score of 54 or more (approximate Snellen equivalent 20/80 or better) and visual field** diameter 10 degrees or more in every meridian of the central field

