Michigan Retinal Degeneration Questionnaire (MRDQ)	Vision Function	The MRDQ is a psychometrically validated patient-reported outcome measure for inherited retinal degenerations questionnaire which consists of fifty-nine (59) questions measuring seven (7) unidimensional domains: central vision, color vision, contrast sensitivity, scotopic function, photopic peripheral vision, mesopic peripheral vision, and photosensitivity.	All	Adults ≥18 years

PROMIS-29® (Patient-Reported Outcomes Measurement Information System®)	Global Physical, Mental, and Social Health	The PROMIS®-29 contains items from seven PROMIS domains: depression; anxiety; physical function; pain interference; fatigue; sleep disturbance; and ability to participate in social roles and activities. The seven domains cover the most relevant areas of self-reported health for most people with chronic illness. There is also one 11-point rating scale for pain intensity.	All	Adults ≥18 years
Visual Symptom and Impact Outcomes Patient Reported Outcome (ViSIO-PRO)	Vision Function and HRQoL	The ViSIO-PRO instrument is designed to assess visual function symptoms, impacts on functional vision, and impacts on wider health-related quality of life (HRQoL). It has been designed for completion by adolescents (12-17) and adults (18+) with retinitis pigmentosa (RP).	All	Adolescents (12-17 years) & Adults (≥18 years)
Visual Symptom and Impact Outcomes Observer Reported Outcome (ViSIO-ObsRO)	Vision Function and HRQoL	The ViSIO-ObsRO instrument is designed to assess visual function symptoms, impacts on functional vision, and impacts on wider health-related quality of life (HRQoL). It has been designed for completion by parents/caregivers of children with retinitis pigmentosa (RP) aged 3-11 years.	All	Children 4-11 years
L. V. Prasad-Functional Vision Questionnaire (LVP-FVQ II)	Vision Function	The LVP-FVQ-II questionnaire consists of 23 questions. The questionnaire is used to assess self-reported difficulties in performing daily tasks in children with visual impairment.	All	Adolescents (12-17 years) & Children (8-11 years)
Ultra-Low Vision Visual Functioning Questionnaire (ULV-VFQ-50)	Vision Function	The ULV-VFQ-50 psychometrically evaluates a visual functioning questionnaire (VFQ) in an ultra-low vision (ULV) population	Vision Cohort 3	Adults ≥18 years

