#### 1116 9.1.1 General Considerations

1117 Both eyes of a participant will be assessed for the main ocular measures of interest. Thus, if there  
1118 are N participants, 2N eyes will be available for analysis. However, outcome measures from two  
1119 (2) eyes of a person are typically strongly correlated ( $r \geq 0.5$ ). The contribution of information  
1120 from the two (2) eyes in this case is  $(2/(1+r))$  instead of two (2). Values for the multiplier to the  
1121 number of participants to obtain an effective sample size are given below in **Table 9-1**. The  
1122 correlation between eyes (inter-eye correlation) for each outcome measure is not known. We  
1123 assume an inter-eye correlation of 0.8 throughout all sample size calculations throughout section  
1124 1.1. This assumption is conservative in that it requires a higher number of participants than lower  
1125 plausible values of r.

1126 **Table 9-1. Multiplier to Obtain Effective N Based on Inter-Eye Correlation**

r	0.0	0.1	0.2	0.3	0.4	0.5	0.6	0.7	0.8	0.9	1.0
Multiplier for Effective N	2.00	1.82	1.67	1.54	1.43	1.33	1.25	1.18	1.11	1.05	1.00

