 1173 visit, **change from baseline to four (4) years** will be considered for sample size  
 1174 justification purposes.
- 1175 ➤ This simplistic approach will produce conservative estimates, in terms of precision.  
 1176 Future work will include exploring impact of sample sizes on these estimates when using  
 1177 all available longitudinal data, for example, how much will this improve precision. This  
 1178 will be documented separately.

1179 **NHS Objective 1 (Natural History)**

- 1180 ➤ **NHS Objective 1** is to characterize the natural history of retinal degeneration associated  
1181 with disease-causing genetic variants over 4 years, using functional, structural, and  
1182 patient-reported outcome measure, **within gene**.
- 1183 ➤ For a given gene, the potential sample size for the gene will impact the precision around  
1184 the point estimates for changes in the outcome measures of interest.
- 1185 ➤ **Table 9-5** provides the half-width of the 95% confidence interval (CI) around the  
1186 estimated percent change in outcome measures under different possible sample sizes and  
1187 standard deviations (SD) of the distribution of the percent change for any given outcome  
1188 measure. The larger the SD and/or the smaller the sample size, the wider the CI, meaning  
1189 the range of possible true values grows.

1190 **Table 9-5. Half-Width of 95% Confidence Intervals Around the Estimated Percent Change**

	Sample Size									
	(effective sample size after adjusting for inter-eye correlation r=0.8)									
	N=10	N=20	N=30	N=40	N=50	N=60	N=70	N=80	N=90	N=100
	(11)	(22)	(33)	(44)	(56)	(67)	(78)	(89)	(100)	(111)
SD=5%	3%	2%	2%	2%	1%	1%	1%	1%	1%	1%
SD=10%	7%	4%	4%	3%	3%	2%	2%	2%	2%	2%
SD=20%	13%	9%	7%	6%	5%	5%	5%	4%	4%	4%
SD=30%	20%	13%	11%	9%	8%	7%	7%	6%	6%	6%
SD=40%	27%	18%	14%	12%	11%	10%	9%	8%	8%	8%
SD=50%	34%	22%	18%	15%	13%	12%	11%	11%	10%	9%
SD=60%	40%	27%	21%	18%	16%	15%	14%	13%	12%	11%

1191

1192 **NHS Objective 2 (Structure-Function Relationship)**

- 1193 ➤ **NHS Objective 2** is to explore whether structural outcome measures can be validated as  
1194 surrogates for functional outcomes in individuals with disease-causing genetic variants,  
1195 **within gene**.
- 1196 ➤ For a given gene, the potential sample size for the gene will impact the precision around  
1197 the point estimates for the correlation between the outcome measures of interest.

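### Table 9-5 applies a two-eye sample-size multiplier to every NHS Objective 1 outcome, including questionnaires scored once per person, and the 20-participant condition counts the gene rather than the people given each instrument

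*Protocol*

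**What the plan says.** Section 1.3 of the protocol sets NHS Objective 1 as describing the within-gene course of disease ("causing genetic variants over 4 years, using functional, structural, and patient"-reported measures), with the condition "Ideally where within-gene sample size is 20 or more". Section 9.1.3 repeats that scope and, in the same list, presents Table 9-5 as the half-width of the 95% confidence interval for percent change, indexed by sample size and by "standard deviations (SD) of the distribution of the percent change for any given outcome" measure. No PRO exception is made, and Objective 1 has no other precision table.

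Each column of Table 9-5 is headed by N and, in brackets, the "effective sample size after adjusting for inter-eye correlation r=0.8". Section 9.1.1 gives the reason for that adjustment: "Both eyes of a participant will be assessed for the main ocular measures of interest". It then extends it without limit: "assume an inter-eye correlation of 0.8 throughout all sample size calculations throughout section" 9.1 (the protocol prints the section number as 1.1).

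The Protocol Outline and sections 4.3 and 6.2 assign the questionnaires by age at baseline and, for one of them, by vision cohort:

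- MRDQ and PROMIS-29: 18 years and over.
- ViSIO-PRO: 12 years and over.
- LVP-FVQ II: 8 to 17 years.
- ViSIO-ObsRO: 4 to 11 years.
- ULV-VFQ-50: adults in Vision Cohort 3.

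**The concern.** The multiplier credits each participant with slightly more than one independent observation because two eyes are measured. A questionnaire score belongs to the person, so there is no second observation to credit. Section 9.1.1 calls the choice of r=0.8 conservative. That is true against lower inter-eye correlations for eye measures, but for a PRO any multiplier above 1.00 errs the other way.

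The second issue is which N is counted. The condition of 20 is applied to the gene, but no instrument is given to all ages in a gene. ViSIO-PRO and ViSIO-ObsRO together span the age range, but they are different instruments with different respondents. In a gene of exactly 20, one participant outside an instrument's age range leaves 19 for that instrument while the gene still qualifies.

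At stake is how a reader judges a gene's sample size for PROs. Taken at the gene's N, Table 9-5 makes PRO precision look better than it can be, slightly so for an instrument given to nearly everyone and materially so for one given to a small subset.

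**Working it through.** **Inputs.** The inter-eye correlation is 0.8 (section 9.1.1). Participant numbers are 10 to 100, with bracketed effective N of 11, 22, 33, 44, 56, 67, 78, 89, 100 and 111, and the SDs are 5% to 60% (Table 9-5).

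**Multiplier.** 2/(1 + r) = 2/1.8 = 1.11, so N=50 becomes 56. Table 9-1 gives 1.00 at r=1.0, which is the value that fits one score per person.

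**Reproducing Table 9-5.** Half-width = t(0.975, n−1) × SD / √n, with n the bracketed effective N.

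- SD 20%, N=50 (n=56): 2.004 × 20 / √56 = 5.36%, printed 5%.
- SD 60%, N=10 (n=11): 2.228 × 60 / √11 = 40.3%, printed 40%.

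All 70 printed entries reproduce this way. With n set to the raw N, only 38 do. The multiplier is therefore built into the table.

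**PRO completed by everyone (multiplier 1.00, n = N).**

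| SD | N | Effective-N half-width | Printed | Raw-N half-width |
|---|---|---|---|---|
| 20% | 50 | 5.36% | 5% | 2.010 × 20 / √50 = 5.68% |
| 30% | 50 | 8.03% | 8% | 2.010 × 30 / √50 = 8.53% |
| 30% | 20 | 13.30% | 13% | 2.093 × 30 / √20 = 14.04% |
| 60% | 10 | 40.31% | 40% | 2.262 × 60 / √10 = 42.92% |

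Across the ten columns the ratio of raw-N to effective-N half-width runs from 1.052 (N=40) to 1.065 (N=10). After rounding, 32 of 70 entries change.

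**PRO completed by a subset.** The protocol gives no within-gene age or vision mix, so the completer counts and the SD of 20% below are assumptions.

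- 35 completers: 2.032 × 20 / √35 = 6.9%
- 25 completers: 2.064 × 20 / √25 = 8.3%
- 10 completers: 2.262 × 20 / √10 = 14.3%

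In a gene of 50, the N=50 column prints 5%. A reader who instead enters the table at N=10 finds 13%, so most of the gap closes once the right n is used. What remains, 14.3% against 13.4% unrounded, is the multiplier.

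**The case against.** The strongest reply is that the protocol never prints a half-width for a questionnaire. The MYO7A example covers only visual acuity, EZ area and static perimetry. The PRO plan in section 9.2.2 is cross-tabulation plus an exploratory generalized linear model, with scoring left to a separate analysis plan. That stands: the precision in question is what Table 9-5 implies for PROs, not a stated PRO figure. It does not remove the point, because section 9.1.3 names PROs in the objective and then offers the table for any outcome.

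It can also be said that the table may be entered at a smaller N, as section 9.1.3 allows for subgroups. That too is largely right, and it makes the subset problem one of which N to read, not of wrong arithmetic. But the note sits under Objective 3, cites Table 9-3, and leads to columns that still carry the multiplier. The remark that plans are written for the majority of outcomes opens section 9.2, not the sample-size section.

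A reader might infer more from the Vision Cohort 3 limit. Since 150 of 1,500 is 10%, a gene at the cap of 100 would seem to hold about 10 ULV-VFQ-50 respondents and could never reach 20. The documents do not support this. Section 2.1 says a maximum of 150 "participants will be enrolled in Vision Cohort 3 (across" genes), caps may be adjusted, and no within-gene share is set for that cohort. A gene with severe disease could supply 20 or more such adults.

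Finally, 20 is an ideal and not a bar. Smaller samples may still be explored, and below 20 the plan turns to case histories.

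**Conclusion.** The point holds at minor severity. Table 9-5 is arithmetically correct for two-eye measures. As worded, it extends a two-eye gain to questionnaires, for which section 9.1.1 gives no justification. With full completion the half-widths should be 5.2% to 6.5% wider in relative terms, which changes 32 of 70 rounded entries. That part rests only on one score per person and the table's own formula.

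The count behind the condition of 20 is the more consequential part. It follows from the age and cohort restrictions alone that a gene can meet the condition while an instrument does not. How far precision falls depends on a mix the protocol does not give, so 6.9%, 8.3% and 14.3% are illustrations at an assumed SD of 20%. For an instrument given to most of a mainly adult gene the loss is modest. It becomes large only where few participants are given the instrument.

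**What to change.** In section 9.1.1 and at Table 9-5 in section 9.1.3, state that the effective N applies only to ocular measures taken in both eyes. For PROs, state that the multiplier is 1.00 and that n is the number of participants given the instrument, and add a raw-n version of Table 9-5. In sections 1.3 and 9.2.2, apply the 20-participant condition to PROs instrument by instrument, with the case descriptions already planned for small samples used below it.

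This takes a few sentences and one recomputed table, with no new data, visits or participants. The cost is that the precision implied for PROs becomes slightly less favourable at full completion, and some instruments in some genes will be reported descriptively.

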**Important Note:**

- **Genes Listed as Variable Mode of Inheritance on RD Rare Gene List**
  - If the site is able to determine the inheritance pattern from the participant’s genetic report\*, the **Genetic Screening Criteria** above may be followed to determine eligibility based on the site determined inheritance pattern.
  - If the site is unable to determine the inheritance pattern from the participant’s genetic report\*, the site should use the most common inheritance pattern to follow the **Genetic Screening Criteria** above. The most common inheritance pattern will be provided to sites for each gene that is listed as having a variable mode of inheritance.
- If there are questions about interpretations of the genetic reports\* prior to the genetic screening phase, the Genetics Committee (GC) and/or the Central Genetics Auditor (CGA) may be consulted. The Coordinating Center (CC) must be contacted first to determine the appropriate mechanism of consultation, consistent with regulatory and consent requirements.

336                   \*Genetic testing will not be performed in this study. A prior conclusive genetic test is  
 337                   what will be assessed for screening analysis.

338                   **2.4.1.2 Ocular Inclusion Criteria**

339                   Both eyes must meet the following criteria at the Registry/Screening Visit to ***enroll into the***  
 340                   ***genetic screening phase.***

- 341                   1. Both eyes must have a clinical diagnosis of retinal dystrophy  
 342                   2. Both eyes must permit good quality photographic imaging (e.g., but not limited to, clear  
 343                   ocular media, adequate pupil dilation, stable fixation)

344                   **2.4.1.3 Participant Exclusion Criteria**

345                   Participants must not meet any of the following exclusion criteria at the Registry/Screening Visit  
 346                   to be eligible to ***enroll into the genetic screening phase.***

- 347                   1. History of more than 1 year of cumulative treatment, at any time, with an agent  
 348                   associated with pigmentary retinopathy including amiodarone, chloroquine,  
 349                   deferoxamine, hydroxychloroquine, pentosan polysulfate, tamoxifen, and deferoxamine

350                   **Note:** Since this is an observational study, pregnant women will not be specifically excluded  
 351                   from participation. **However, minors that are pregnant shall be precluded from**  
 352                   **participation until they become the age of majority.**

353                   **2.4.1.4 Ocular Exclusion Criteria**

354                   If either eye has any of the following ocular exclusion criteria at the Registry/Screening Visit,  
 355                   then the participant is not eligible to ***enroll into the genetic screening phase.***

- 356                   1. Current vitreous hemorrhage  
 357                   2. Current complications of pathological myopia (for example, but not limited to, myopic  
 358                   maculopathy including atrophy, scar, choroidal neovascularization, schisis) that could  
 359                   inhibit ability to obtain good quality photographic imaging

- 360 3. History of intraocular surgery (for example, but not limited to, cataract surgery,  
 361 vitrectomy, penetrating keratoplasty, or LASIK) within 3 months of Registry/Screening  
 362 Visit
- 363 4. Current or any history of confirmed diagnosis of glaucoma (for example, but not limited  
 364 to, glaucomatous VF changes or nerve changes, or history of glaucoma filtering surgery)
- 365 5. Current or any history of retinal vascular occlusion or proliferative diabetic retinopathy
- 366 6. History or current evidence of ocular disease that, in the opinion of the Investigator, may  
 367 confound assessment of visual function (for example, but not limited to, tractional or  
 368 rhegmatogenous retinal detachment, any vitreoretinal surgery, retinal vascular occlusion,  
 369 proliferative diabetic retinopathy)
- 370 7. The following medications and treatments are prohibited as they can affect progression of  
 371 retinitis pigmentosa (RP). The participant must not have received the following  
 372 treatments:
- 373 ♦ Any use of ocular stem cell or gene therapy
  - 374 ♦ Any treatment with ocriplasmin
  - 375 ♦ Treatment with Ozurdex (dexamethasone), Iluvien, or Yutiq (fluocinolone acetonide)  
 376 intravitreal implant
- 377 8. The following medications and treatments are excluded **within the specified timeframe**:
- 378 ♦ Treatment with an ophthalmic oligonucleotide **within the last 9 months** (last  
 379 treatment date is less than 9 months prior to Registry/Screening Visit date)
  - 380 ♦ Treatment with any other product **within five times the expected half-life** of the  
 381 product (time from last treatment date to Registry/Screening Visit date is at least 5  
 382 times the half-life of the given product)

#### 383 2.4.2 Registry/Screening Visit Data Collection and Testing

384 The following procedures will be performed at the Registry/Screening Visit. An overview of the  
 385 equipment and certification requirements for all testing is in section 6.1. All Registry/Screening  
 386 Visit testing procedures must be completed within ninety (90) days of the Registry/Screening  
 387 Visit date, unless specified below. All ocular testing will be performed in each eye, right eye  
 388 (OD) first and then left eye (OS). Screening procedures will last approximately two (2) hours.  
 389 The testing procedures are detailed in the **Uni-Rare Clinical Site Manual of Procedures**.

